- a) Candidates to primary BS undergoing laparoscopic gastric bypass (LGBP) or laparoscopic sleeve gastrectomy (LSG) from September 2020 to September 2022. This group will be evaluated prior to surgery (a period vulnerable to biases by the request for surgery that affect the answers to the questionnaires for fear of being contraindicated for surgery). The subjects of this group will be followed at 4 months, 1 year, 3 years and 5 years after BS.
- b) A control group of subjects with obesity not candidates to BS matched with the intervention group for age, sex and BMI prior to BS.

*The control group will be recruited by each investigator (10 subjects) and will be evaluated once. According to our casuistic, in order to be comparable with the REGAINSEEN

Versión 2, 07/03/2019

intervention group 80% should be women of 45 years of age with a BMI $> 40 \text{ kg/m}^2$. This group is needed to adjust for variables such as motivation, patient expectations related to surgery and the effect of surgery.

Inclusion criteria:

- Candidate to primary BS from 09/2010 to 09/2021.
- Subjects with obesity ($\geq 40 \text{ kg/m}^2$) not candidates to BS.
- Internet users.
- Primary BS: LGBP and LSG.
- Accept to participate in the study and provide signed informed consent.

Exclusion criteria:

- Second time and/or revisional BS.
- Pregnancy.
- Presence of intellectual impairment impeding the administration of the psychometric tools.
- Type 1 diabetes.
- Dyslexia.

Weight variables: definitions.

- a) The different weight variables will be calculated as follows:
 - Weight lost (kg): Pre-BS weight – weight at nadir.
 - Current weight lost: Pre-BS weight - current weight.
 - Ideal weight: weight corresponding to a BMI = 25 kg/m^2 .
 - Excess weight lost (%): $(\text{Pre-BS weight} - \text{current weight})/\text{excess weight} [(\text{pre-BS weight} - \text{ideal weight}) \times 100]$.
 - Total weight lost (%): $(\text{pre-BS weight} - \text{current weight}/\text{pre-BS weight}) \times 100$.
- b) To study WR the following variables will be calculated:
 - Total WR (%): $(100/(\text{pre-BS weight} - \text{weight at nadir})) * \text{weight regained (kg)}$.
 - Excess WR (EWR %): $[(\text{current weight} - \text{weight at nadir})/\text{excess weight}] \times 100$
 - Weight regained (Kg): current weight – weight at nadir.

Excess weight lost $> 50\%$, total weight lost $> 25\%$ and Excess weight regain $> 15\%$ will be considered as significant.

Psychological evaluation:

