Additionally, 100 controls not undergoing BS will be included and matched for age, gender and BMI with the objective of standardising the values in the scales. The ratio will be 1:4 for controls and patients undergoing BS, respectively.

Statistical analysis

The design and statistical analysis of the present study meet the recommendations of consensus documents in the literature [25]–[28], specially the TRIPOD statement [29]. A statistical analysis plan (SAP) will be elaborated [30] prior to finalisation of data collection and will provide an in depth description of the statistical methods to be used, the tables and figures that will be included in the statistical report as well as the

strategy to follow in the case of missing values [31], [32], and multiplicity [33] adapted to regulatory [34] and scientific recommendations [26].

Descriptive statistics will be used according to standard calculation methods [35]. To elaborate a predictive model to a determined time, logistic regression models will be used [36]–[39]. For time variables up to a determined event, survival analysis techniques will be used. The function of survival as well as the median of time to the event (confidence interval of 95% [CI 95%]) will be estimated using the Kaplan-Meier method. Estimations of risk will be made with the classical [40] and extended [41] Cox proportional hazards model. Covariables will be tested for the assumption of proportional hazards. Initially all the possible covariables will be analysed in a univariate analysis, and factors with $p < 0.1$ will be included in a multivariate model. All the variables not selected for inclusion ($p \geq 0.1$) will, in turn, be checked in the final model to determine whether their inclusion would improve adjustment of the model by a p value < 0.1 or a value less than Akaike. Continuous variables will be tested as continuous linear variables, categorical variables (that is, quartile and predefined for clinical reasons) or continuous non-linear variables based on previously published literature, clinical value and goodness-of-fit models.

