The following is a summary of the general approach of inferential statistical analysis. The Fisher exact test will be used to compare categorical variables. For continuous variables between the two groups, the Student's t test and ANOVA for more than two will be used. In the case of not fulfilling the assumptions of applicability or of ordinal variables, non-parametric methods (Mann-Whitney U test or Kruskall-Wallis) or an ANOVA will be used with previous transformation of the dependent variable to ranges to evaluate more than one factor concomitantly (rank-ANOVA).

Variables repeated over time will be analysed as follows: (i) continuous variables, such as the evolution of the variables of weight, with longitudinal mixed model for repeated measurements (MMRM)[42], [43]; (ii) Binary variables will be analysed using Generalised Linear Mixed Models (GLMM). Marginal models will be used (Generalised Estimating Equation (GEE) for the analysis of sensitivity [44][45].

The results will be analysed with the SAS version 9.4 statistical package (or a higher version) [46] (SAS Institute Inc., Cary, NC) or with equivalent validated software. The level of significance will be bilateral at 5%.

Ethical Committee

The protocol should be approved by the Ethical Committees of the participating centres. An informed consent sheet will be included together with the project for presentation to the Ethical Committee of each centre. Informed consent will include special emphasis on the confidentiality of the personal data and that these data will not be able to be identified. Following receipt of approval, the investigators must send a copy of the approval and the number assigned for incorporation in the project file. The original should remain in the centre and its safety is the responsibility of the centre investigator.

The results of the centres that do not obtain approval from the Ethical Committee will not be used in the analyses.

Treatment of missing data

Missing data will be registered in box x to ensure that the data cannot be recovered. If the box remains empty, there will continue to be doubt about whether the data can be recovered.

References

- [1] P. Bjorntorp *et al.*, "Obesity : Preventing and Managing the Global Epidemic," *WHO Tech. Rep. Ser.*, p. 253, 2000.
- [2] A. P. Courcoulas *et al.*, "Long-term outcomes of bariatric surgery: A National Institutes of Health symposium," *JAMA Surg.*, vol. 149, no. 12, pp. 1323–1329, 2017.

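### The control group is matched on age, sex and BMI by a coarse profile, but no adjustment for these factors is named for comparing scale scores with surgical patients

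*Combined protocol and SAP*

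**What the plan says.** Design describes controls with obesity who are not surgical candidates, "matched with the intervention group for age, sex and BMI prior to BS". Matching is described as a target profile: "intervention group 80% should be women of 45 years of age with a BMI" above 40 kg/m². Recruitment is by quota: "The control group will be recruited by each investigator (10 subjects) and will be evaluated once". No pairs, sets, calipers or set identifier are described.

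Two purposes are given. Design states: "This group is needed to adjust for variables such as motivation, patient expectations related to surgery and the effect of surgery". The Sample size section says the 100 controls are "matched for age, gender and BMI with the objective of standardising the values in the scales", and adds: "The ratio will be 1:4 for controls and patients undergoing BS, respectively".

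The Statistical analysis section gives a general summary of inferential methods. For categorical variables it names Fisher's exact test. For continuous variables: "For continuous variables between the two groups, the Student's t test and ANOVA for more than two will be used". If assumptions fail, it offers rank-based tests or a rank-ANOVA that can take more than one factor. Mixed models are reserved for variables repeated over time. No sentence names age, sex or BMI as covariates for the control comparison.

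**The concern.** Matching at recruitment does not by itself give a valid or efficient comparison; the analysis has to carry the matching factors too. An independent-sample test ignores them. Where matching is loose, the remaining differences in age, sex and BMI pass into the group difference on every scale. Where matching is good, the variance those factors explain stays in the error term and precision is lost.

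Loose matching is plausible. The profile is coarse and filled in blocks of 10 per investigator. The Inclusion criteria require a BMI of at least 40 kg/m² for controls but state no BMI floor for surgical candidates. At stake is the interpretation of the scale values against the reference group, which is what the controls were recruited for.

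**Working it through.** **The plan's own figure.** Sample size gives 80% power at two-sided 5% for a standardised difference of 0.281 with 400 completers. A two-sample calculation needs 199 per group (normal approximation) or 199.8 (exact t), so 400 in total, and 400/0.9 = 444.4, rounded up to 445. The figure therefore reproduces as 200 v 200 within the surgical cohort. It is not a calculation for 100 controls v 400 surgical patients.

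**Standard error of the control comparison, in SD units.** √(1/100 + 1/400) = 0.1118. With all 445 surgical patients at baseline it is 0.1107, so the choice matters little. The unadjusted detectable difference at 80% power is 2.80 × 0.1118 = 0.313 SD.

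**Case A: matching is loose.** Bias = imbalance × effect of the factor on the scale. Assume a 10-point difference in the proportion of women and a 0.5 SD sex difference: 0.10 × 0.5 = 0.05 SD.
- Bias/SE = 0.05/0.1118 = 0.447.
- Type I error = 1 − Φ(1.96 − 0.447) + Φ(−1.96 − 0.447) = 0.073.

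A simulation (4,000 runs per setting, 100 v 400, one covariate) took a larger assumed imbalance of 0.3 SD:

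| Variance explained by covariate | t test, type I error | Adjusted model, type I error |
|---|---|---|
| 5% | 8.7% | 4.9% |
| 10% | 12.8% | 5.1% |
| 30% | 28.6% | 5.5% |

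**Case B: matching is good.** Let R² be the share of scale variance explained by age, sex and BMI. The documents do not give it. The correct standard error is 0.1118 × √(1 − R²). The unadjusted interval is too wide by 1/√(1 − R²) − 1, and the unadjusted test's true type I error is 2 × [1 − Φ(1.96/√(1 − R²))].

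| R² | Correct SE | Interval too wide by | True type I error | Detectable difference, adjusted |
|---|---|---|---|---|
| 0 | 0.112 | 0% | 5.0% | 0.313 |
| 0.05 | 0.109 | 3% | 4.4% | – |
| 0.10 | 0.106 | 5% | 3.9% | 0.297 |
| 0.20 | 0.100 | 12% | 2.8% | 0.280 |

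The gain at R² 0.10-0.20 equals 1/0.9 to 1/0.8, that is 11-25% more subjects. In the simulation with close matching and no imbalance, the t test rejected in 5.2%, 4.2% and 2.0% of runs at 5%, 10% and 30% explained variance, and the adjusted model in 5.8%, 5.1% and 4.8%. At 5% explained variance the simulation shows no conservatism. It appears at 10% and above.

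**The case against.** The strongest reply is that the plan never says this comparison will be made by t or Fisher tests. The text is a general summary, and the quoted sentence may only distinguish two groups from more than two. The controls may serve purely as a reference for standardising scales. Sample size foresees 4-7 covariates, Statistical analysis describes a multivariable procedure, and a fuller SAP is still to be written.

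Much of this stands. A reader might infer that the plan has prescribed a wrong test; the documents support only that no adjusted method is named for this comparison. The general provisions do not fill that gap. Sample size names no covariates. The multivariable procedure is set out with the logistic and Cox models and screens covariates at p < 0.1, so age, sex and BMI could be dropped. The confounders listed under Psychological evaluation do not include them. Rank-ANOVA is only a fallback.

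A reader might also infer that the intervals are simply wrong, or that a paired analysis has been omitted. Neither is supported. No matched sets are described, so there may be nothing to condition on. With good matching the unadjusted test is conservative, which costs precision and does not create false positives.

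Finally, the numerical inputs are assumed. The milder example yields a bias of only 0.05/0.313, about 16% of the detectable difference.

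**Conclusion.** The point holds as an unspecified adjustment with a clear better choice. The plan matches on three factors and names no analysis that uses them. The more serious consequence is residual imbalance: type I error of about 7% under the mild assumed example, and more under larger assumed imbalances. The lesser one is lost precision: intervals about 3-12% too wide if the factors explain 5-20% of variance, and no loss at 0%. The two arise under opposite matching conditions and should not be added together.

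A reader might infer that the study's main results are at risk. The documents do not support that. The objective and the primary variable concern weight trajectory after surgery, within the surgical cohort, and the control comparison is supportive.

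**What to change.** In the SAP:
- State whether matching is by frequency or individual, and which surgical assessment is compared with the single control assessment.
- Specify that surgical-versus-control comparisons of the scales use linear regression (logistic or ordinal where the scale requires it) on group, with age, sex and BMI forced in and exempt from the p < 0.1 screen.
- Keep t and Fisher tests for descriptive tables.
- Use a conditional or set-stratified analysis only if individual matched sets are actually formed. A set identifier would then have to be added, because the datasheet under Data collection lists centre, patient code and case/control status but no set.

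Age, sex, and baseline weight and height are already in the datasheet for both groups. The cost is SAP wording, plus one datasheet field if sets are used.

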These data will be used to calculate the absolute WL, % of WL, EWL, BMI lost, the total weight regained (TWR) and the EWR .

Surgery: 0: GBP, 1: LSG

Date of surgery: This will be registered as a date and is in order to adapt the dates of the follow-up visits to the different times.

Follow-up: at 4-6 months, and 1, 3 and 5 years

Diabetes yes/no; diabetes treatment (0: no; 1: metformin, 2: DPP4 inhibition, 3: iSGLT2, 4: Sulfonylureas , 5: GLP-1 analogues, 6: insulin). Likewise, combined treatment

should be separated with a comma. For example, a patient controlled with metformin + iSGLT2 would be 1,3.

AHT yes/no; AHT treatment (0: no; 1: treatment with 1 drug; 2: treatment with > 2 drugs);

Dyslipidaemia: 0: No, 1: Yes; treatment: 0: no, 1: Treatment with statins, 2: treatment with fibrates, 3: treatment with statins + ezetimibe.

Sleep apnoea hypopnoea syndrome (SAHS) yes/no; Use of CPAP yes/no;

Revision surgery: 0: no, 1: yes.

Date of revision surgery: registered in date format.

Analytical parameters: fasting glucose, insulin, HbA1c, creatinine, total cholesterol, HDL.

Bioimpedance: fat mass (FM) %; FM kg; fat free mass: (whatever is available).

Sample size

The study will include 445 patients undergoing BS. It is estimated that the percentage of losses to follow-up at 5 years will not be greater than 10% and thus, at least 400 patients must achieve complete follow-up. This sample size will have a statistical power of 80% for detecting an effect size, that is, differences divided by the standard deviation of at least ≥ 0.281 [11]–[13] in magnitude; this effect size is considered in the literature as being of small magnitude [14], [15], and consequently the statistical power will be greater for greater magnitudes. The study will also be discriminatory for binary variables presenting an association with an odds ratio (OR) of at least ≥ 1.78 [11], [16], [17]. Finally, correlations ≥ 0.6 [18]–[21] will be detected considering that values < 0.5 are not relevant. In the three cases cited the calculations of sample size were made using a bilateral level of significance of 5% and a statistical power of 80%. This sample size will allow adjusting possible confounding factors and generate a multivariate model with a minimum number of covariates (at least 4-7, depending on the final number of events and correlations) to obtain adjusted estimators [22]–[24].

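### No unequal-variance test is named for the control-versus-surgery comparison (100 v about 400), where Student's t and its rank fallback both miss the 5% level if the groups differ in spread

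*Combined protocol and SAP*

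**What the plan says.** The summary of inferential methods in the Statistical analysis section assigns Student's t test to continuous variables in two groups and ANOVA to more than two. For failed assumptions and ordinal variables it continues: "In the case of not fulfilling the assumptions of applicability or of ordinal variables, non-parametric methods (Mann-Whitney U test or Kruskall-Wallis"), and the same sentence adds a rank-ANOVA for several factors at once. It names neither a Welch or Satterthwaite version nor the check that decides whether assumptions hold. The section ends with the error rate: "The level of significance will be bilateral at 5" per cent.

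The Sample size section plans for 445 surgery patients, at least 400 of them followed to the end, and 100 matched controls. On the allocation it says: "The ratio will be 1:4 for controls and patients undergoing BS, respectively". The Design section has controls evaluated once, so a questionnaire comparison between controls and patients falls under the t test and rank-test rule. Mixed models are reserved for variables repeated over time. The Data collection section also lists follow-up weights for controls; if those are collected, repeated weight falls under the mixed model and outside this point.

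**The concern.** Student's t test, on its usual reading, pools the two variances. With equal group sizes that does little harm. With 100 against 400, the pooled variance is mostly that of the larger group, while the true variance of the mean difference depends mostly on the smaller group. If controls are the more variable group, the standard error is too small and false positives exceed 5%. If they are the less variable group, the standard error is too large and power is lost. Switching to Mann-Whitney reduces this but does not remove it, because the usual variance of the rank statistic also assumes identical distributions under the null. At stake is whether the stated 5% level means what it says when questionnaire scores are compared between controls and patients.

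**Working it through.** **The plan's own figure.** The Sample size section claims 80% power for "differences divided by the standard deviation of at least ≥ 0.281", with "a bilateral level of significance of 5% and a statistical power of 80" per cent. The noncentral t distribution with 200 v 200 gives a detectable effect of 0.2808 and power of 80.05% at 0.281, so the figure reproduces for an even split of 400. The inflation also reproduces: 400/0.90 = 444.4, rounded up to 445. At 100 v 400 with equal SDs, the same calculation gives a detectable effect of 0.314 and 70.8% power at 0.281. So 0.281 does not describe the control comparison, which is a separate observation.

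**Inputs.** n1 = 100 controls and n2 = 400 patients (Sample size); two-sided 5% (Statistical analysis). The ratio r = SD(control)/SD(surgery) is an assumption, because the documents give no SDs. Data are normal with equal means.

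**Pooled t, analytic.**

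- Pooled variance of the difference: [((n1−1)r² + (n2−1))/(n1+n2−2)] × (1/n1 + 1/n2)
- True variance of the difference: r²/n1 + 1/n2
- Size ≈ 2[1 − Φ(1.96 × pooled SE/true SE)]

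At r = 1.5 the pooled variance is (99 × 2.25 + 399)/498 × 0.0125 = 1.2485 × 0.0125 = 0.01561. The true variance is 0.0225 + 0.0025 = 0.0250. The SE ratio is √(0.01561/0.0250) = 0.790, and the size is 2[1 − Φ(1.549)] = 0.12.

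At r = 0.8 the pooled variance is (99 × 0.64 + 399)/498 × 0.0125 = 0.01161. The true variance is 0.0064 + 0.0025 = 0.0089. The SE ratio is 1.142, and the size is 0.025.

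**The plan's rule, simulated.** The plan names no assumption check. A median-centred Levene test at 5% is assumed, with Mann-Whitney if it rejects and t otherwise. The two-step column gives the range over separate simulations of several thousand replicates each (6,000 and 8,000 in two of them). The Monte Carlo standard error near 0.07 with 8,000 replicates is √(0.07 × 0.93/8000) ≈ 0.003.

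| SD ratio | Pooled SE / true SE | t alone | Mann-Whitney alone | Two-step rule | Welch |
|---|---|---|---|---|---|
| 0.75 | 1.185 | 0.02 | 0.03 | 0.031–0.032 | about 0.05 |
| 0.8 | 1.142 | 0.024 | 0.034 | 0.032 | 0.049 |
| 1 | 1.000 | 0.051 | 0.051 | about 0.05 | 0.051 |
| 1.25 | 0.876 | 0.086 | 0.067 | 0.066–0.077 | 0.050 |
| 1.5 | 0.790 | 0.119 | 0.081 | 0.085–0.091 | 0.048 |

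Across all runs at ratios 0.75 to 1.5, Welch lay between 0.044 and 0.053. At r = 1.5 the Levene check rejected in 99.6% of runs, so the rule is almost always Mann-Whitney there and still gives about 9%. A one-factor rank-ANOVA has the same size as Mann-Whitney. Ordinal scores go straight to the Mann-Whitney column.

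**Balanced groups.** At 200 v 200 and ratios 0.5 to 2, the t test stays at 4.8% to 5.2% and Mann-Whitney at 5.0% to 6.0%. The distortion therefore comes mainly from the 1:4 imbalance.

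**Power.** At r = 0.75 and a difference of 0.25 surgery-group SDs, power is 0.67 for t, 0.71 for the two-step rule and 0.79 for Welch. With equal SDs and a difference of 0.281, Welch has 0.697 against 0.705 in one simulation and 0.708 against 0.714 in another.

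**The case against.** **The plan does not apply t regardless.** It moves to rank methods when assumptions fail, and equal variance is one of them. A reader might take the t-alone rates of 8.6% and 12% as the plan's error rates. The documents do not support that, since at a ratio of 1.5 the t test would almost never be used. This objection stands, and the two-step column is the one to use. It lowers the size of the problem without removing it.

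**The documents do not show unequal spread.** A reader might infer it from the Design section, which warns of "biases by the request for surgery that affect the answers to the questionnaires" among candidates, and from the control profile: "intervention group 80% should be women of 45 years of age". The first says that answers are biased, not that scores are compressed. The second is given to make controls comparable with patients, and a set age, sex and BMI profile does not imply a narrow range of questionnaire scores. If both effects were real they would push the SD ratio in opposite directions. Unequal spread is therefore a possibility to guard against, not a finding.

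**The null matters.** Mann-Whitney is valid as a test that two distributions are identical. It misses 5% only when read as a test of equal centre, which is how a score comparison is normally reported.

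**Scope.** A reader might extend the point to patients with weight regain against the rest. The documents give no such split, and they assign prediction at a fixed time to logistic regression and time to event to Cox models. The extension is not supported.

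**Deferral.** The protocol promises a later SAP with fuller methods. That does not settle the matter, because the current text already names a test and fallbacks, and nothing in it signals a change.

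**Conclusion.** The concern holds for single-time comparisons of controls with surgery patients, and it is minor. As written, the rule does not secure the 5% level for a difference in centre if the SDs differ. Over assumed ratios of 0.75 to 1.5 its size runs from about 3% to about 9%. These figures rest on normal data, the 100 v 400 sizes and a Levene check that the plan does not specify. The direction of any error cannot be predicted from the documents, which favours a test that is valid either way. Near-balanced comparisons are barely affected. The mixed-model analysis of weight and the logistic and Cox models are outside the claim, and so is the study's main objective, which concerns weight trajectory within the surgery group.

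**What to change.** In the Statistical analysis section and the SAP, make Welch's t test the default for two-group comparisons of continuous variables and Welch ANOVA the default for more than two groups, with no preliminary variance test. For two-group ordinal scores, the Brunner-Munzel test may replace Mann-Whitney; in simulation at 100 v 400 its size was 4.8%, 5.4% and 5.4% at SD ratios 0.75, 1.25 and 1.5. If Mann-Whitney is kept, state that it tests identical distributions.

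The cost is about a sentence of text and standard software. The only statistical price is a loss of under one percentage point of power if the SDs are equal (about 0.70 against 0.71 at a difference of 0.281).

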Although the mean data support the effectiveness of BS in the treatment of obesity, the magnitude of WL and the maintenance of weight reduction after BS notably differ among individuals, even among those undergoing the same surgical technique [3]. Data from the pivotal Swedish Obese Subjects (SOS) study show that the maximum WL after BS ranged between -95.5 and + 2.0 kg, and weight regain (WR) after nadir was between 0.0 and 51.4 kg[4]. This heterogeneity in weight trajectory leads some patients to present lower WL than expected and/or the recovery of an important amount of weight after nadir.

At present, it is recognised that the magnitude and maintenance of WL are important to the health results of BS. However, one of the main problems encountered is how to define insufficient WL and pathological WR after BS. A systematic review described that the most frequent definition used for insufficient WL after primary BS is a WL < 50% of the excess weight present prior to surgery with or without a body mass index (BMI) > 35 kg/m² at 18 months after surgery [5]. Thus, insufficient WL is not just the absolute WL but rather the deviation of WL from the result that is usually achieved after BS.

Likewise, in relation to the definition of WR, several studies have used different definitions based on kilograms, units of BMI, or percentage of excess WL regained after nadir or at different time points, including: regain of 10 kg, regain of 25% of excess WL; regain of 15% of initial WL; regain of 5 kg/m²; any WR with a BMI >35 kg/m² at nadir, at 18 months or 3-5 years post-BS [6]. Patients who show WR present a relapse of not only obesity but potentially also the co-morbidities which had remitted during the initial WL. In this case many require revisional surgery or a second procedure to re-achieve WL, either with RYGB, or another procedure such as duodenal switch at the expense of adding a malabsorptive component to the surgical process, which risks extra complications and a high rate of nutritional deficiencies (Annex 1).

The variability of WL or WR has been associated with a wide range of factors related to the surgical technique used, psychological factors, behavioural, dietetic factors, physical activity and comorbidities as well as biological factors which regulate food intake, energy storage and expenditure [7]. Variables such as previous weight, age and the type of surgery explain between 40-50% of the variance in WL, with the rest

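### The weight models do not prespecify procedure, age or pre-surgery weight, which the plan itself credits with 40-50% of the variance in weight loss

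*Combined protocol and SAP*

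**What the plan says.** **Known determinants.** The Introduction reports that "Variables such as previous weight, age and the type of surgery explain between 40-50% of the variance in WL".

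**Two operations, one group.** The Inclusion criteria admit "Primary BS: LGBP and LSG", and the Design section places both in a single surgical group. Data collection codes study group only as control or case, but records the operation separately ("Surgery: 0: GBP, 1: LSG"). Age, height and baseline weight are recorded too.

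**Sample size.** "The study will include 445 patients undergoing BS", and "at least 400 patients must achieve complete follow-up". No split by procedure is given. The section says the sample permits adjustment for possible confounders, with at least 4-7 covariates in a multivariable model. It names none.

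**Weight model.** The Statistical analysis section assigns "continuous variables, such as the evolution of the variables of weight, with longitudinal mixed model for repeated measurements (MMRM") and stops there. It lists no fixed effects, interactions or covariance structure. The t test, ANOVA and Fisher test in the same section are given without covariates.

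**Covariate selection.** Earlier in that section, directly after the logistic and Cox models, all candidate covariates are to be screened one at a time at p < 0.1. Those left out are then re-checked by p < 0.1 or Akaike. The rule is not tied to the MMRM. Further detail is deferred to a later SAP.

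**Named confounders.** The list under Psychological evaluation and in Table 1 consists of psychological, behavioural and social measures. Procedure, age and pre-surgery weight are not on it.

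**The concern.** The objective is the association of eating pattern and psychological variables with weight trajectory after surgery. The plan names the strongest known determinants of weight loss and collects them, but does not commit to adjusting for them. Two things are at stake.

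- **Precision.** Variance that known covariates could explain may stay in the residual, which widens every interval for a behavioural association.
- **Interpretation.** The documents describe no random allocation of procedure. If the mix of operations differs between patients with high and low scores on an eating scale, an unadjusted association carries part of the operation's effect. Without a procedure-by-visit term, the model also imposes one common time profile on both operations.

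Leaving the choice to a univariate screen means that the adjustment set is unknown until the data are seen, and that it can differ between outcomes and visits.

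**Working it through.** **1. Reproduce the plan's figures.**

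Inputs from Sample size: two-sided 5%, 80% power, "differences divided by the standard deviation of at least ≥ 0.281", 400 completers, 10% loss. Assumption: the 400 split 200/200 on the exposure, since no split is stated.

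- Power = Φ(d × √(n/2) − 1.960), with n per group. This is Φ(0.281 × √100 − 1.960) = Φ(0.850) = 80.2%. The t-test version gives 80.0%.
- Enrolment = 400/(1 − 0.10) = 444.4, rounded up to 445.

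Both agree with the plan. The sample size does not depend on covariate adjustment.

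**2. Effect of adjusting for the three terms.**

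Input from the Introduction: R² of 0.40 to 0.50. Residual SD = √(1 − R²), in units of the unadjusted SD. Detectable difference = 0.281 × residual SD. Power at 0.281 = Φ(2.81/residual SD − 1.960).

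| R² | Residual SD | Detectable difference (unadjusted SD) | Power at 0.281 |
|---|---|---|---|
| 0 | 1 | 0.281 | 80.2% |
| 0.40 | 0.775 | 0.218 | 95.2% |
| 0.50 | 0.707 | 0.199 | 97.8% |

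The last two rows are the best case, for four reasons.

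- The 40-50% concerns weight loss, and two of the four primary weight measures are regain.
- Total and excess weight lost (%) already divide by a quantity built on pre-surgery weight, so part of that effect is removed.
- The Introduction gives the three variables as examples, so they may not account for the whole figure.
- The calculation takes one continuous outcome at one time and an exposure uncorrelated with the covariates.

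**3. Results by procedure.**

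The split between operations is not given, so a range is assumed. Within a stratum, the exposure is again split equally.

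| Stratum's share of 400 | Patients | Detectable difference (SD) | Power at 0.281 |
|---|---|---|---|
| 30% | 120 | 0.516 | 34% |
| 50% | 200 | 0.398 | 51% |
| 70% | 280 | 0.336 | 65% |

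The detectable exposure-by-procedure interaction is 2.8016 × √(4/n₁ + 4/n₂), where n₁ and n₂ are the numbers per procedure. With 200 and 200 it is 0.560 SD, and with 120 and 280 it is 0.611 SD. By-procedure results can therefore only be exploratory.

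**4. Confounding by procedure.**

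For a continuous outcome the size would be roughly (difference in outcome between procedures) × (difference in procedure share between exposure groups). The documents give neither factor, nor an SD to scale the result, so no figure is offered.

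**The case against.** **Silence is not exclusion.** A reader might infer that the weight model omits these variables. The documents do not support that. The MMRM sentence names no terms at all, not even visit or the exposure. It sits in what is introduced as a summary, with detail deferred to a later SAP. This part of the objection stands: the defect is lack of prespecification.

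**The plan does provide for adjustment.** Sample size foresees adjusted estimates, and the screen covers all candidate covariates. A strong determinant would usually pass. Suppose, for illustration, that the procedures differ by 0.3 SD among 400 patients. The chance of p < 0.1 is then about Φ(0.3 × √100 − 1.645) = 0.91 with equal numbers, and Φ(0.3 × √84 − 1.645) = 0.865 with a 30/70 split. This answers only part of the point. The rule is not tied to the MMRM, it calls for no procedure-by-visit term, and it leaves the adjustment set to the data when the plan already names the factors that matter.

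**The confounder list is not exhaustive.** It is labelled as psychological, so the absence of procedure, age and weight from it does not show an intention to ignore them. That is right.

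**Matching.** Matching controls on age, sex and BMI concerns the comparison of operated patients with controls. It does nothing for associations within the operated group.

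**Stronger readings.** A reader might also infer that procedure choice follows eating pattern, that the two operations take different courses over five years, or that a common time course fits neither. The documents say nothing on how the operation is chosen and give no results by procedure. These are reasons to include the terms. They are not findings.

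**Conclusion.** The point holds as a gap in prespecification, and it is worth closing. The plan credits three recorded variables with 40-50% of the variance in weight loss, but commits to none of them, nor to procedure-by-visit, in its analysis of weight. Forcing them in is a better method than univariate screening and needs no new data.

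The gain is at best a fall in the detectable difference from 0.281 to 0.218-0.199 SD with 400 completers. This rests on an equal exposure split, an exposure unrelated to the three covariates, and the full 40-50% applying to the outcome analysed. It should not be assumed for the regain measures. Confounding by procedure is plausible but of unknown size. The sample size calculation is not called into question.

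**What to change.** State the following in the Statistical analysis section or the later SAP, before outcome data are examined.

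1. In operated patients, every MMRM, GLMM/GEE, logistic and Cox model of a weight outcome includes procedure (LGBP or LSG), age and pre-surgery weight (or BMI) as fixed terms, whatever their p values. Any data-driven selection applies only to further covariates.
2. The repeated-measures models (MMRM and GLMM/GEE) also include procedure-by-visit. The logistic model at a fixed time and the standard Cox model have no visit factor, so the term does not apply there.
3. The exposure-by-procedure interaction, with estimates by procedure, is secondary and exploratory. Its low power is stated.

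**Cost.** Wording only, since all three variables are already collected. With four follow-up visits the MMRM spends at most 1 + 1 + 1 + 3 = 6 degrees of freedom, which is little against about 400 patients. The price is higher in the event-based models. Three forced terms use three of the stated minimum of 4-7 covariates, leaving 1-4 at that minimum for eating and psychological variables. The number of events should be checked against this before those models are fixed.
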